5.0 Study Design*

5.1 *Describe and explain the study design (e.g. case-control, cross-sectional, ethnographic, experimental, interventional, longitudinal, observational).*

Response: The experiment protocol involves a maximum of ten sessions and will take two or three hours for each session. Baseline data will be collected before the first session for both overground and treadmill walking. During this session, the sound level will be adjusted based on the feedback received from the users. The researcher will ask the comfortable sound level to the participant before starting the experiment. Training will be conducted on the treadmill with the cable-actuated device for about 20 minutes. When the cables were removed, participants walked on the treadmill for 4 minutes during the post-training session. During training and post-training, participants will be exposed to feedback while walking on the treadmill. After treadmill walking, CP participants will be asked to take a ten-minute break and then practice overground walking for two minutes with auditory feedback (type A) and without it (type B). Effects of 3 different types of

auditory feedback will be explored namely, rhythmic sounds, movement sonification, and sound notifying erroneous gait. Group A participants will be further divided into groups depending on the type of auditory feedback that will be provided. Participants will participate in a maximum of 10 sessions, two or three times a week. Before the first and after the last training, participants will be evaluated for functional gait assessment, 6-min-walk, leg strength using a dynamometer, international physical activity questionnaire (short form), usability questionnaire, and Modified Ashworth test by a physical therapist.

6.0 Study Intervention/Investigational Agent

1.1 Description: *Describe the study intervention and/or investigational agent (e.g., drug, device) that is being evaluated.*

Response:

A cable-actuated system that can apply a therapeutic force while walking was developed in our past study. The system consists of motorized cables, belt, and tension sensors to apply a downward force to strengthen the legs. During the training, participants powered soleus muscles more and changed the coordination of gastrocnemius muscles. Six children with crouch gait and diplegia participated in the experiment for 15 sessions. After 15 sessions, six children with CP presented better foot clearance, heel-toe pattern, and straighter walking posture during the stance. These children also showed immediate change when the cables were removed by recalibrating their CNS against the downward force. To walk against the resistance force, children provide feedforward control of their anti-gravity muscles to create larger upward force. When the cables were removed, they still kept the increased muscle force which resulted in stronger stride, heel-toe pattern, and foot clearance [1]

Our smart insoles have shown the capability to provide a full gait monitoring strategy during daily life [2]. This system is fully portable and equipped with pressure sensors, an IMU, a microcontroller, a Bluetooth module, and a battery. An array of pressure sensors is integrated into the insole to measure the pressure distribution with an IMU to provide the posture of the foot. The device can provide spatiotemporal gait parameters, pressure distribution, the center of pressure, and foot clearance with a wireless system and mobile application. The unique design of the pressure sensor allows detecting abnormal foot contact with the ground which is typically found in patients with a neurological movement disorder. The shoe was tested on stroke patients and the elderly to monitor their gait patterns in real-time. Using the insole, we will measure the gait characteristics of the individuals such as gait parameters, ground reaction force, the center of pressure to provide auditory feedback [3]. An instrumented treadmill manufactured by Bertec will also be used as a backup in case we face technical issues with the smart insole [4]. The instrumented treadmill allows for highly accurate 6-axis load measurement for each lower limb.

Furthermore, using the data from the smart insole and Bertec Force plate instrumented treadmill, three different types of auditory feedback will be provided to the selected participants. The sound level of the auditory feedback is adjustable and will be determined based on the user's feedback during the baseline trials. Rhythmic auditory feedback will be generated to provide participants information about the cadence which will help them synchronize their footsteps. Another type of auditory feedback consists of, an unpleasant sound which will be generated in case the gait characteristics such as knee flexion or ankle plantarflexion of the participants abnormal. The last type of auditory feedback will comprise modulating the characteristics such as pitch and tempo of the sound to reflect the motion of the lower limbs[5]. Analyzing the effects of these different types of auditory feedback will not only allow us to identify if auditory feedback aids in the retention of benefit from strength training for a longer duration but also identify the varying degrees of effects of different types of auditory feedback on retention of gait adaptations from cable actuated robot.

- [1] J. Kang, D. Martelli, V. Vashista, I. Martinez-Hernandez, H. Kim, and S. K. Agrawal, "Robot-driven downward pelvic pull to improve crouch gait in children with cerebral palsy," *Sci. Robot.*, 2017, doi: 10.1126/scirobotics.aan2634.
- [2] Yang, Zhuolin, et al. "A smart environment-adapting timed-up-and-go system powered by sensor-embedded insoles." *IEEE Internet of Things Journal* 6.2 (2018): 1298-1305.
- [3] Yang, Zhuolin, et al. "A smart environment-adapting timed-up-and-go system powered by sensor-embedded insoles." *IEEE Internet of Things Journal* 6.2 (2018): 1298-1305.
- [4] Instrumented Treadmills, URL:- <https://www.bertec.com/products/instrumented-treadmills>
- [5] Schaffert, Nina, et al. "A review on the relationship between sound and movement in sports and rehabilitation." *Frontiers in psychology* 10 (2019): 244.

6.1 Drug/Device Handling: If the research involves drugs or device, describe your plans to store, handle, and administer those drugs or devices so that they will be used only on subjects and be used only by authorized investigators.

- *If the control of the drugs or devices used in this protocol will be accomplished by following an established, approved organizational SOP (e.g., Research Pharmacy SOP for the Control of Investigational Drugs, etc.), please reference that SOP in this section.*

Response: N/A

6.2 If the drug is investigational (has an IND) or the device has an IDE or a claim of abbreviated IDE (non-significant risk device), include the following information:

- Identify the holder of the IND/IDE/Abbreviated IDE.
- Explain procedures followed to comply with sponsor requirements for FDA regulated research for the following:

| FDA Regulation | Applicable to: | | |
|----------------|----------------|-------------|-------------------------|
| | IND Studies | IDE studies | Abbreviated IDE studies |
| 21 CFR 11 | X | X | |
| 21 CFR 54 | X | X | |
| 21 CFR 210 | X | | |
| 21 CFR 211 | X | | |
| 21 CFR 312 | X | | |
| 21 CFR 812 | | X | X |
| 21 CFR 820 | | X | |

Response: N/A

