of training with a cable-actuated robot will be provided. The device will augment 15% of their own body weight. While they are walking with the device, auditory feedback will be provided for the participants who are assigned to the auditory group. The auditory and non-auditory groups will be randomly assigned. Furthermore, one of the 3 different types of auditory feedback will be randomly assigned to participants from the feedback group. A break of 5 minutes will be provided after 10 minutes of walking with the device. After the robotic training is completed, the device will be taken off and the participant will walk without the device to monitor the immediate retention of the training. After every 10 minutes, the researcher will ask the participant questions as per the Borg exertion scale to check the fatigue of the participant. After finishing the treadmill session, participants will take a 10-minute break and walk 4 minutes with (or without auditory feedback) on the floor. The participant will repeat overground walking for a total of three sets. There will be a total of ten training sessions, two or three sessions a week and each session will last for a maximum of 3 hours. In addition, pre and post-training visits are required to evaluate functional gait assessment, 6-min-walk, leg strength using a dynamometer, international physical activity questionnaire (short form), usability questionnaire, and Modified Ashworth test by a physical therapist.

12.2 Describe what data will be collected.

NOTE: For studies with multiple data collection points or long-term follow up, consider the addition of a schedule or table in your response.

Response:

- We will schedule the participants to visit the lab. We will make a table when the participants are available.
- *EMG data from the muscles*
- *Vicon motion capture data*
- *Photo and Video of the test*
- *IMU sensor data*
- *Smart insole data*
- *Ground reaction force*

12.3 List any instruments or measurement tools used to collect data (e.g. questionnaire, interview guide, validated instrument, data collection form).

Include copies of these documents with your submission.

Response: Vicon motion capture system, Delsys Trigno sEMG system, and Bertec Force plate instrumented treadmill, Smart Insole

12.4 Describe any source records that will be used to collect data about subjects (e.g. school records, electronic medical records).

Response: N/A

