19.0 Data Management and Analysis*

19.1 *Describe the data analysis plan, including any statistical procedures. This section applies to both quantitative and qualitative analysis.*

Response: The collected motion capture data will be labeled and filtered with a 4th order Butterworth filter. All sEMG data will be post-processed by bandwidth filter, enveloped, smoothed, and scaled. To define the beginning and the end of each repetition the speed of the markers is used as a threshold. The data will be time-scaled and averaged over different trials.

The analyses for CP subjects are carried out separately. Descriptive statistics will be obtained to compare the randomized groups on baseline factors including pre-existing chronic conditions, underlying disease, demographics, and other potential confounders. When the numeric data are not normally distributed based on graphic inspection (e.g., normal quantile plots), we will consider the Box-Cox transformation. For numeric data, a mixed-effects model will be constructed, where

major factors include the effect of time within each day, the effect of feedback, the effect of the day as well as the effect of the random assignment. Major statistics to obtain will be improvement measures between baseline and the end of treatment. An appropriate covariance structure will be considered reflecting the correlations within subjects. Various contrasts will be tested to see an improvement by the major factors. Some other covariates such as demographic and other subjects characteristics can be included in the models if a significant difference is shown. Residual plots will be examined to check the normality of the residual. If not normally distributed, we will consider simpler nonparametric methods that compare specific factor combinations in a form of various contrasts. For categorical data, we will construct a similar model to the numeric data, except that we will use an appropriate link function based on the generalized linear model. The covariance structures will be incorporated into the analysis using a generalized structural equation modeling strategy. For this pilot study, we do not consider controlling family-wise Type I error as the purpose of the study is to see the viability of the treatment and potentially support the bigger clinical trials in the future.

19.2 If applicable, provide a power analysis.

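### The 80% power in section 19.2 does not follow from its stated inputs (about 56% two-sided), and section 6.0 promises more about the three feedback types than 3 to 4 people per type can show

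*Combined protocol and SAP*

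**What the plan says.** **Power.** Section 19.2 gives 20 participants, 10 per group, and says an effect size of 0.5 then has 80% power at alpha 0.05 in a two-group comparison. It assumes six repeated measures under compound symmetry with correlation 0.1. It does not give the sidedness, the SD that the 0.5 refers to, the outcome, or which six measurements are meant.

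**Analysis.** Section 19.1 plans a mixed model whose factors include "the effect of feedback, the effect of the day as well as the effect of the random assignment". It adds: "Various contrasts will be tested to see an improvement by the major factors". The main statistics are improvements from baseline to the end of treatment. The study is called a pilot, and family-wise error is not controlled.

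**Feedback types.** Section 6.0 says the analysis will "identify the varying degrees of effects of different types of auditory feedback on retention of gait adaptations from cable actuated robot". Section 5.1 is milder: the three kinds of "auditory feedback will be explored namely, rhythmic sounds, movement sonification, and sound notifying erroneous gait". It continues: "Group A participants will be further divided into groups depending on the type of auditory feedback that will be provided". Section 12.1 says "one of the 3 different types of auditory feedback will be randomly assigned to participants from the feedback group". Hypothesis 2 in section 2.2 concerns auditory feedback as such and does not mention types.

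**Who receives feedback.** Section 12.1 says "The auditory and non-auditory groups will be randomly assigned". Section 5.1 can be read as each participant doing both, because participants "practice overground walking for two minutes with auditory feedback (type A) and without it (type B". The grant aim and section 2.1 refer to eight adults. The study summary, 7.1 and 19.2 give 20.

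**The concern.** The power statement is the only quantitative justification of the sample size, and 19.1 says the study may support larger trials. If 80% is overstated, a null result on feedback will be read as stronger evidence against it than it is, and the figure may be carried into the next design.

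Section 6.0 adds a promise about feedback types that the power statement does not cover: it addresses two groups of 10, while types divide one of those groups in three. It is also unclear which contrast tests hypothesis 2. Section 19.1 lists feedback and random assignment as separate factors, and 5.1 and 12.1 can be read as different designs (within and between participants).

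**Working it through.** **Inputs from 19.2:** n = 10 per group, effect d = 0.5, alpha = 0.05, m = 6 measures, compound symmetry with correlation r = 0.1. **Assumed, because not stated:** d is in SDs of a single measure, the outcome is each person's mean of the six measures, and the test is two-sided unless noted.

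**1. The plan's own figure.**
- SD of a six-measure mean = sqrt((1 + (m − 1)r)/m) = sqrt((1 + 5 × 0.1)/6) = sqrt(0.25) = 0.50.
- Standard error of the group difference = 0.50 × sqrt(1/10 + 1/10) = 0.2236.
- Noncentrality = 0.5/0.2236 = 2.236.
- Two-sided t, 18 df, critical value 2.101: power 56.2%. Normal approximation: 60.9%.
- One-sided t, critical value 1.734: 69.4%. Normal approximation: 72.3%.
- Effect with 80% power, two-sided: 0.66 (t) or 0.63 (normal).
- Group size for 80% at 0.5, two-sided t: 17 (80.7%); 16 gives 78.1%.

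The stated 80% is not reproduced.

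**2. Could another reading give 80%?**
- 0.5 in SDs of the six-measure mean: 18.5%.
- Effect size read as Cohen's f = 0.5: about 99%. With f = 0.25: 56% between groups, 55% for group by time.
- Correlation 0, two-sided normal: 78.2%.
- First-order autoregressive correlation 0.1, one-sided: 80.9% (normal) or 78.2% (t).

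The last two come close but contradict the stated compound symmetry with 0.1.

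**3. If the outcome is improvement from baseline, as 19.1 says** (same d and r, two-sided t, one of the six taken as baseline):
- Last minus first: variance 2(1 − 0.1) = 1.80, SD 1.342, standard error 0.600, noncentrality 0.833, power 12%.
- Mean of five later measures minus baseline: variance (1 + 4 × 0.1)/5 + 1 − 2 × 0.1 = 1.08, SD 1.039, standard error 0.465, noncentrality 1.076, power 17%.
- Mean of five with baseline as covariate: variance 0.28 − 0.1² = 0.27, standard error 0.232, noncentrality 2.152, power 53%.

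**4. Correlation above 0.1.** For the six-measure mean, r = 0.3 gives SD 0.645 and 37.5% power; r = 0.5 gives SD 0.764 and 28.3%. Last minus first moves the other way: at r = 0.5 its variance is 2 × 0.5 = 1.00 and power is 18.5%.

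**5. Between two feedback types.** Ten people over three types is 3/3/4 if balanced. The six-measure mean is used again, d = 0.5, two-sided t. The lower df use only the two types compared; 16 df pools the residual over four groups (20 − 4).

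| Comparison | Standard error | Noncentrality | Power | 95% CI half-width |
|---|---|---|---|---|
| 3 v 3, 4 df | 0.408 | 1.225 | 15.9% | 1.13 |
| 3 v 3, 16 df | 0.408 | 1.225 | 21.1% | 0.87 |
| 3 v 4, 5 df | 0.382 | 1.309 | 18.8% | 0.98 |
| 3 v 4, 16 df | 0.382 | 1.309 | 23.4% | 0.81 |

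The difference detectable with 80% power is 1.14 to 1.54. If all 20 received feedback (one reading of 5.1), types would be 7/7/6 and power 38% to 42%. If eight were the feedback arm (3/3/2), 2 v 3 would have 12% to 18%.

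**The case against.** **This is a pilot.** Section 19.1 gives up family-wise control for that reason, and a pilot need not reach 80% power. That stands: neither more participants nor a multiplicity correction is needed. But a power figure that is stated should follow from its inputs.

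**Unwritten assumptions may lie behind 80%.** Sidedness and effect-size unit are missing, so an undisclosed basis cannot be excluded. This is why stating that basis is an acceptable alternative to changing the figure.

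**56% does not describe the improvement measure in 19.1.** Correct. It applies to the mean of the six measures, so any restated figure must name its outcome.

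**The claim about types is one verb in the intervention description.** Largely fair. No hypothesis concerns types, 5.1 says explored, and 19.2 powers only two groups. What remains is a wording conflict. The 3/3/4 split is also assumed: 12.1 says only that types are randomly assigned. Under simple randomisation, 3/3/4 arises in about 21% of draws, and some type has at most one person in about 31%.

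**A stronger reading is tempting.** A reader might infer that all pairs of types will be tested and one type chosen for a later trial. Uncorrected pairwise tests would flag at least one pair about 12% of the time when types are equal, and significant results at a true 0.5 would average about twice that value. The documents do not support that reading. Section 19.1 neither names type as a factor nor specifies pairwise type tests, and no section says a type will be selected or dropped.

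**Conclusion.** The power statement needs correcting. On the inputs in 19.2, with 0.5 in single-measure SDs and the six-measure mean as outcome, power is 56% to 61% two-sided or 69% to 72% one-sided. For a simple change from baseline at correlation 0.1 it is about 12% to 17%. No dropout allowance is stated, and 22.3 destroys withdrawn participants' data, so achieved power may be lower.

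The point about types is real but smaller: section 6.0 goes beyond 5.1, and 16% to 23% power (balanced split, two-sided t, same inputs) cannot support it. A reader might conclude that every statement about types must be barred. The documents do not require that; an exploratory label with intervals is enough for a pilot.

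The design conflict between 5.1 and 12.1, and eight against 20, must be settled because they determine which comparison the power describes and how many people each type has.

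**What to change.** 1. **19.2:** state about 56% power at 0.5, or 0.66 detectable with 80% power, two-sided, for the mean of six measures in single-measure SD units. If another outcome is intended, recalculate for it. Alternatively, state the assumptions that give 80%. In either case name the sidedness, effect-size unit and outcome.
2. **6.0:** say that type-specific results are exploratory and will be reported with confidence intervals, in line with 5.1.
3. **5.1 and 12.1:** reconcile overground walking with and without feedback with the randomised auditory and non-auditory groups.
4. **19.1:** if 12.1 stands, name the randomised comparison of all feedback types pooled v no feedback as the test of hypothesis 2, with its outcome and time point.
5. **Grant aim and 2.1:** reconcile eight adults with 20.

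The cost is protocol text only, with no added participants or visits. The downside is a less favourable stated power and a weaker claim about feedback types.

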7.0 Local Number of Subjects

7.1 Indicate the total number of subjects that will be enrolled or records that will be reviewed locally.

Response: 20

7.2 If applicable, indicate how many subjects you expect to screen to reach your target sample (i.e. your screen failure rate).

Response:

7.3 Justify the feasibility of recruiting the proposed number of eligible subjects within the anticipated recruitment period. For example, how many potential subjects do you have access to? What percentage of those potential subjects do you need to recruit?

Response: Cerebral Palsy is the most common of all childhood disabilities, affecting approximately three live births out of every thousand in the United States. With the population of Erie County being over 900,000, it is feasible to identify 20 adults with CP to participate in the study.

8.0 Inclusion and Exclusion Criteria*

8.1 *Describe the criteria that define who will be **included** in your final study sample.*

NOTE: This may be done in bullet point fashion.

Response: The inclusion criterion for the study is adults with cerebral palsy (18-65 years old) who can ambulate a distance of 100 feet with or without the use of assistive devices. However, they shouldn't need physical assistance from a caregiver while they walk 100 feet.

8.2 *Describe the criteria that define who will be **excluded** from your final study sample.*

NOTE: This may be done in bullet point fashion.

Response: Recruited participants will be excluded if they have severe Equinovarus foot or Genu recurvatum of the knee. Participants who had surgery within 6 months will be excluded. Individuals with pregnancy, lower limb prosthetics, severe respiratory problems such as chronic obstructive pulmonary disease, heart disease, a loss of sensation, uncontrolled blood pressure, a seizure disorder, severe arthritis will be excluded from this study.

8.3 *Indicate specifically whether you will include any of the following special populations in your study using the checkboxes below.*

NOTE: Members of special populations may not be targeted for enrollment in your study unless you indicate this in your inclusion criteria.

Response:

- Adults unable to consent
- Individuals who are not yet adults (infants, children, teenagers)
- Pregnant women
- Prisoners

8.4 *Indicate whether you will include non-English speaking individuals in your study. Provide justification if you will exclude non-English speaking individuals.*

*In order to meet one of the primary ethical principles of equitable selection of subjects, non-English speaking individuals may **not** be routinely excluded from research as a matter of convenience.*

In cases where the research is of therapeutic intent or is designed to investigate areas that would necessarily require certain populations who may not speak English, the researcher is required to make efforts to recruit and include non-English speaking individuals. However, there are studies in which it would be reasonable to limit subjects to those who speak English. Some examples include pilot studies, small unfunded studies with validated instruments not available in other languages, studies with numerous

questionnaires, and some non-therapeutic studies which offer no direct benefit.

Response: We will exclude non-English speaking individuals as we don't have human resources for translation. All instructions should be equally provided to the user for consistency.

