Deterioration of locomotion skills is a major problem in persons with CP. This can lead to a sedentary lifestyle at an early age and a significant decrease in the quality of life [4]. A few studies have addressed progressive resistive strength and aerobic training in adults with CP which show significant strength improvements in their walking ability and gait parameters [5]. As an extension of these studies, we investigated the use of targeted gait training using a cable-actuated system over a treadmill that promoted strengthening during walking in children with CP [6]. This cable-actuated system provided downward force and participants had to extend their legs against the force while walking on a treadmill. This leads to a straighter walking posture, longer stride, and reduced toe-walking pattern in a supervised environment. Once the participants were taken out of the actuated cable system, they showed immediate improvement of knee extension and heel-to-toe walking. This is because participants recalibrated their movement to walk against the downward force and its effect lasted for a while after the force was removed. This after-effect of adaptation may be used in physical therapy to let the patients experience a more normal movement pattern [7]. In the proposed study, we will introduce the use of instrumented insoles to provide feedback to sustain positive after-effects in unsupervised ecological environments. Sensory feedback has been shown to improve the gait features of individuals with cerebral palsy in the past [8, 9, 10]. We will use similar methods to assist adults with CP to retain the positive motor adaptation from using the cable-actuated system on the treadmill. We will collect pressure data, foot clearance, heel-to-toe pattern from smart insoles and provide feedback to the participant on their gait pattern. We

hypothesize that once participants have experienced gait in response to resisted gait training, the feedback from the insoles will assist them to maintain the improved gait. Furthermore, we hypothesize that the use of sensory feedback with minimal supervision will lead these individuals to take an active role in their gait training. It can foster collaboration between the therapist and participant in the shared goal of improved gait quality. These are essential components of self-management, especially important for individuals with chronic conditions like cerebral palsy.

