10.0 Eligibility Screening*

10.1 Describe **screening procedures** for determining subjects' eligibility.

Screening refers to determining if prospective participants meet inclusion and exclusion criteria.

Include all relevant screening documents with your submission (e.g. screening protocol, script, questionnaire).

Response: [name] is a licensed physical therapist. She will perform screening procedures for the patients. We will examine the individual's ability to ambulate 100 feet with or without assistive devices but not with the assistance of a caregiver to ensure independent walking through the protocol.

N/A: There is no screening as part of this protocol.

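### Entry ignores gait pattern and assignment is not stratified on it, so at 10 v 10 the kinematic retention comparison (hypothesis 2) is exposed to chance imbalance that the covariate rule in 19.1 would usually miss

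*Combined protocol and SAP*

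**What the plan says.** **Who enters.** Section 8.1 asks for "adults with cerebral palsy (18-65 years old) who can ambulate a distance of 100 feet with or without the use of assistive devices", without physical help from a caregiver. Section 8.2 removes some gait patterns: "Recruited participants will be excluded if they have severe Equinovarus foot or Genu recurvatum of the knee". The only walking test described at screening (10.1) is the "ability to ambulate 100 feet with or without assistive devices but not with the assistance of a caregiver". Nothing in 8.1, 8.2 or 10.1 requires crouch, toe-walking or any other deviation, or distinguishes one-sided from two-sided cerebral palsy.

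**What the intervention aims at.** Section 4.1 describes the earlier effect of the downward pull: "This leads to a straighter walking posture, longer stride, and reduced toe-walking pattern in a supervised environment". The earlier evidence in Section 6.0 is narrow: "Six children with crouch gait and diplegia participated in the experiment for 15 sessions". One of the three sounds, the unpleasant one, "will be generated in case the gait characteristics such as knee flexion or ankle plantarflexion of the participants abnormal".

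**Assignment and analysis.** Section 12.1: "The auditory and non-auditory groups will be randomly assigned". It then randomises one of three sounds within the feedback group. No stratification is stated. Section 12.2 lists motion capture, EMG, insole and force data, but no cerebral palsy type or gait class. Section 19.1: "Major statistics to obtain will be improvement measures between baseline and the end of treatment". It compares the groups descriptively at baseline, including on underlying disease, and allows subject characteristics into the models only once a significant difference has appeared. Section 19.2 sets 20 participants, 10 per group.

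**The concern.** Hypothesis 2 in Section 2.2 is about retention, and Section 3.0 makes lower-body motion one of the two primary measures. A person, or a leg, whose stance knee and foot contact are already close to normal may show little kinematic correction after training and so may have little to retain, with or without sound. If such participants gather in one group, the auditory v non-auditory difference in a knee or foot-contact measure reflects the gait mix as well as the feedback. The pilot is meant to inform larger trials, and either a spurious difference or a hidden one would mislead that decision. The protection in 19.1 depends on a significance test that has little chance of reacting with 20 people.

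**Working it through.** **Inputs.** From 19.2: 20 participants, 10 per group, test size 0.05. From 12.1: random assignment, no strata. Assumed: the number K of the 20 with little baseline deviation. The documents give none, so K = 4, 6 and 10 are shown.

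**The plan's own figure.** The plan has no figure on gait mix. The nearest is the 80% power in 19.2. With effect 0.5 SD and six measures under compound symmetry 0.1, the mean of six has variance (1 + 5 × 0.1)/6 = 0.25, so SD 0.5. The standard error of the difference is 0.5 × √(2/10) = 0.224, and 0.5/0.224 = 2.236. Two-sided power is Φ(2.236 − 1.96) = 61%, not 80%. That is a separate matter. It is noted here only because it means that no power figure should be built on the 80%.

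**Chance of an uneven split.** With 10/10 assignment, the number X of such participants in one group is hypergeometric: P(X = x) = C(K, x) × C(20 − K, 10 − x) / C(20, 10), where C(20, 10) = 184,756. For K = 6:

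- 5 v 1, either way: 2 × 6 × 2,002 / 184,756 = 13.0%
- 6 v 0, either way: 2 × 1 × 1,001 / 184,756 = 1.1%
- difference of 4 or more: 14.1%
- difference of 2 or more: 1 − (20 × 3,432 / 184,756) = 63%

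| K of 20 (assumed) | Differ by 2 or more | Differ by 4 or more | Fisher two-sided p when they differ by exactly 4 |
|---|---|---|---|
| 4 | 58% | 9% | 0.09 (4 v 0) |
| 6 | 63% | 14% | 0.14 (5 v 1) |
| 10 | 66% | 18% | 0.18 (7 v 3) |

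**Would 19.1 react?** Section 19.1 does not say which difference must be significant, or at what level. Read as a test of group imbalance at 0.05, it reacts to none of the splits in the last column. With equal groups, Fisher's two-sided p is the probability of a split at least that uneven, so the rule can react only to splits that are themselves rare. For K = 6 that leaves only 6 v 0 (p = 0.011).

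**What a 5 v 1 split does.** Let D be the difference in mean retained kinematic change between participants with and without the deviation. If feedback has no effect, the expected group difference given that split is (5/10 − 1/10) × D = 0.4 D. A 4 v 2 split gives 0.2 D. The documents give no value for D.

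**Dilution, as a bound.** If a share q has exactly zero feedback effect, the mean group difference shrinks to (1 − q) of its intended size: 0.8 at q = 20%, 0.7 at q = 30%. Zero effect is the worst case, so these are upper bounds on the loss.

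**The case against.** The strongest reply is that the plan does not depend on crouch or toe-walking.

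- Hypothesis 1 covers walking ability as well as posture, and Section 24.1 expects gains in step length, walking speed or single stance time. Section 3.0 adds muscle activation, leg strength and the 6-minute walk. None of these needs a gait fault.
- Section 6.0 describes the after-effect as retained anti-gravity muscle force, and nothing says that this fails in straighter walkers.
- Only one of the three sounds is an error signal, so about 3 to 4 of the 10 auditory participants receive it. Rhythmic sound and sonification need no fault.
- Broad entry suits a pilot in an understudied population.
- Chance imbalance affects any prognostic factor at 10 v 10, and the error rate of a randomised comparison already allows for it.

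Most of this stands, and it rules out three stronger readings. A reader might infer that both hypotheses are diluted. The documents do not support that for hypothesis 1, whose other outcomes are open to everyone and which has no between-group contrast. A reader might infer a definite loss of power. The share is unknown and zero effect is a limiting case. A reader might infer that entry should be restricted to a gait pattern. The stated aims do not require it, and it would need a gait assessment at screening that is not planned.

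What the reply does not answer is precision. An error rate that is valid on average over randomisations does not make one unbalanced 10 v 10 result easy to interpret, and the needed baseline information will already have been recorded.

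**Conclusion.** The point holds for the kinematic retention outcomes of hypothesis 2, and as a cheap improvement rather than a flaw that invalidates the design. Gait pattern is plausibly prognostic for those outcomes, yet it is neither an entry condition, a stratum nor a prespecified covariate. Under the assumed 6 of 20, a difference of 4 or more arises in 14% of randomisations (9% to 18% for 4 to 10 of 20), and the 19.1 rule, read as an imbalance test at 0.05, passes over a 5 v 1 split. This rests on three assumptions: the share, an exact 10/10 split, and that participants with little deviation retain less kinematic change. The documents make the last plausible but do not show it.

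**What to change.** Keep entry as broad as it is, and make these changes:

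1. From the overground and treadmill baseline recording that 5.1 already plans before the first session, record for each participant the gait deviation and whether the cerebral palsy is one- or two-sided. Add both to 12.2.
2. Define one yes/no gait-deviation factor and write its cut-off before enrolment. The protocol sets no limit for what counts as abnormal, so this has to be supplied. In 12.1, stratify the auditory/non-auditory assignment on that factor alone. Groups of 3 to 4 per sound are too small to stratify further; describe their gait mix instead.
3. In 19.1, replace the significance-triggered rule with prespecified adjustment for that factor or, preferably, for the baseline value of each kinematic outcome.
4. State the rule that names the analysed leg at baseline.

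Cost: assignment must wait until the baseline recording has been read, group sizes may not come out at exactly 10 and 10, and the model uses one more degree of freedom (18 becomes 17 in a simple two-group comparison of 20). The rest is protocol and SAP wording; no new walking test is needed.
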